**ADAS – Word Recall**  
**SAMPLE FORM – Page 2 of 4**

Center Name	Patient Number	Patient Initials	Examiner Initials	Examination Date														
	P R - 

			

				

			

				

			

				

					

 Month Day Year					

**Present Word List #2.**

Check **EACH** word correctly recalled.

TRIAL 1	
BOTTLE	
POTATO	
GIRL	
TEMPLE	
STAR	
ANIMAL	
FOREST	
LAKE	
CLOCK	
OFFICE	

**TOTAL**

--

TRIAL 2	
FOREST	
TEMPLE	
BOTTLE	
STAR	
POTATO	
GIRL	
CLOCK	
ANIMAL	
LAKE	
OFFICE	

**TOTAL**

--

TRIAL 3	
GIRL	
TEMPLE	
POTATO	
ANIMAL	
FOREST	
LAKE	
OFFICE	
CLOCK	
BOTTLE	
STAR	

**TOTAL**

--

Indicate total number of words correctly recalled for EACH trial on the ADAS Cognitive Behavior Form.

**12. Executive Function (Maze):**

--	--

number of errors

--	--

time at completion or second error  
(total seconds)

**13. Number Cancellation:**

--	--

number of targets hit  
(Range: 0 - 40)

--	--

number of errors

--	--

number of times to remind of task

If any item(s) 1-13 are incomplete or not done, please specify reason:

Subject too cognitively impaired to complete

Subject was unable to complete for physical reasons

Subject refused

Not Done, for reason other than above explain: \_\_\_\_\_

\_\_\_\_\_

\_\_\_\_\_

\_\_\_\_\_

Alzheimer's Disease Cooperative Study

**ADAS – Delayed Recall**  
**SAMPLE FORM – Page 3 of 4**

Center Name	Patient Number P R -   	Patient Initials   	Examiner Initials   	Examination Date    Month Day Year
-------------	---	--	---	--

**Instructions:** Say to the patient, "NOW I WANT YOU TO TRY TO REMEMBER THE WORDS THAT I SHOWED YOU EARLIER ON PRINTED CARDS. CAN YOU TELL ME ANY OF THOSE WORDS?"

Allow a maximum of two minutes for recall.

check EACH word correctly recalled.

BOTTLE	
POTATO	
GIRL	
TEMPLE	
STAR	
ANIMAL	
FOREST	
LAKE	
CLOCK	
OFFICE	

**TOTAL**

**ADAS – Word Recognition**  
**SAMPLE FORM – Page 4 of 4**

Center Name	Patient Number	Patient Initials	Examiner Initials	Examination Date
	P R -   - 	  	  	   /    /   
				Month Day Year

**Present Word List #2.**

Check subject's response for each word. Subject should respond "yes" to original words which are bolded. INCORRECT responses are shaded. Three trials of reading and recognition are given.

[figure not shown]
	Yes	No
COST		
NATION		
CHIMNEY		
SPARROW		
DAMAGES		
TRAFFIC		
SANDWICH		
SERVICE		
SHELL		
SOLUTION		
YARD		
TUBE		
BODY		
GROUND		
STICK		
ENGINE		
RICHES		
GRAVITY		
SUMMER		
WISDOM		
MAN		
MEAL		
PASSENGER		
ACID		

	Yes	No
BATTLE		
MUCH		
TUBE		
TEAM		
COPY		
ENGINE		
GRAVITY		
COST		
JAR		
DISTANCE		
TRIUMPH		
TEMPER		
SENTENCE		
FOX		
PASSENGER		
SANDWICH		
SOLUTION		
WHISTLE		
CHIMNEY		
UNION		
ACID		
MEAL		
DAMAGES		
RICHES		

[figure not shown]
	Yes	No
VISITOR		
ACID		
SPEAK		
SOLUTION		
NAME		
MEAL		
LINE		
BILL		
CHIMNEY		
ENGINE		
WEALTH		
TUBE		
IMAGE		
COST		
SANDWICH		
DAMAGES		
ELEPHANT		
RICHES		
GRAVITY		
FUTURE		
PASSENGER		
STRING		
BANNER		
BERRY		

[figure not shown]
\*see procedures manual for further clarification

IRB NUMBER: 2017-471  
IRB APPROVAL DATE: 11/09/2018

[figure not shown]

[figure not shown]
IRB NUMBER: 2017-471  
IRB APPROVAL DATE: 11/09/2018

[figure not shown]
IRB NUMBER: 2017-471  
IRB APPROVAL DATE: 11/09/2018

**Example**

A2

## Example for use with versions A, B, and C

"6" and "1"

1 2 2 4 5 9 5 6 6 9 1 9 6 7 8 3 2 4 3 7 2 1 4 2 2 1 2 6 6 3

"2" and "8"

6 2 6 7 2 3 1 3 8 5 5 5 8 1 7 9 1 7 2 7 4 5 7 6 1 3 9 6 2 1

9 4 6 9 5 7 1 8 9 5 6 5 4 2 7 1 5 2 7 9 1 7 1 1 4 2 8 5 8

1 9 7 9 7 1 6 7 8 6 5 5 7 2 9 6 5 9 5 4 7 3 2 4 5 6 1 4 3 4

4 6 8 4 1 4 1 7 2 4 7 1 7 6 7 5 4 9 8 7 5 6 2 1 6 9 3 1 4 8

7 8 6 7 1 7 1 3 4 3 9 8 6 5 1 8 3 4 2 6 9 9 6 1 6 4 3 9 3 4

4 9 3 8 7 2 5 4 4 8 7 6 4 1 4 7 2 6 8 7 5 6 3 2 6 4 4 6 8 4

4 8 3 4 7 5 4 4 7 9 7 3 6 8 6 5 4 7 4 3 4 9 2 5 3 5 4 7 3 5

4 9 3 3 8 1 8 4 2 6 5 6 1 7 2 4 2 9 7 9 7 6 1 5 1 4 1 9 8

## INTRODUCTION

The test items on the cognitive part of the **ADAS** should be given in the order indicated.

**The WORD RECALL test is given first**  
and the  
**WORD RECOGNITION task is given last**  
with the  
**other cognitive tests given in-between.**

Separating the two word memory tasks in this way minimizes the chance that a subject will confuse the words from the two tasks.

At the start of a test session, before giving the **WORD RECALL** test, the tester should have a short conversation with the subject about neutral topics such as the weather, the subject's trip to the clinic, or what the subject had for breakfast. This conversation will help to put the subject at ease before the testing begins and will give the tester an opportunity to observe how the subject can use and understand language.

➲ There are three clinical ratings of language ability on the cognitive part of the **ADAS**.

The **ADAS** is not a timed test and the subject's score does not depend upon how rapidly the test is completed. The cognitive items should be given so that the session moves smoothly and quickly, but not so that the subject feels pressured to respond rapidly.

Feedback to the subject should be neutral and, usually, should not indicate whether or not the response was correct. Comments such as, "**That's fine**" or "**You're doing well**" are appropriate as long as the subject is trying. If the subject specifically asks whether or not they were correct, feedback can be given.

TABLE OF CONTENTS	PAGE
Word Recall Task.....	2
Naming Task .....	3 - 4
Commands .....	5
Constructional Praxis .....	6 - 7
Ideational Praxis .....	8
Orientation .....	9
Word Recognition .....	10 - 11
Remembering Test Instructions .....	12
Spoken Language Ability .....	13
Word-Finding Difficulty and Comprehension .....	14

## INSTRUCTIONS for WORD RECALL TASK

**On this task, the subject is given three trials to learn a list of high-frequency, high-imagery nouns. The 10 words are printed in block letters on white cards.**

Use the appropriate word list for each visit as indicated on the study worksheet, and record the subject's responses on the study worksheet.

At the start of the first trial, the tester gives instructions similar to the following:

**“I am going to show you some words printed on these white cards one at a time. Please read each word out loud and try to remember it, because later I will ask you to try to remember all of the words I have shown you. Ready, read the word and try to remember it.”**

The examiner can prompt with:

**“Read it out loud and try to remember it”** as necessary.

If the subject cannot read the word or is slow, the examiner can say the word out loud and have the subject repeat it. Note this and continue with this procedure at each testing. In some cases, the examiner may have to say all of the words and have the subject repeat them. Regardless, make sure the subject looks at each word while repeating it.

After the presentation, the tester asks the subject to try to recall as many of the words as possible by saying:

**“Good, now tell me all the words you remember that were on the list.”**

Two more learning and recall trials follow.

For trials 2 and 3, say to the subject:

**“Now I’m going to show you that same list again. Read each word out loud and try to remember it.”**

Encouragement can be given if the subject is nervous or giving up.

### SCORING:

**The subject’s score is the mean number of words not recalled on three trials (maximum score = 10)**

**Enter the subject’s score on the study worksheet**

# ADAS

## INSTRUCTIONS for NAMING TASK

**For this task, the subject is asked to name the 12 randomly presented real objects, with high (Flower, Bed, Whistle, Pencil), medium (Rattle, Mask, Scissors, Comb), and low (Wallet, Harmonica, Stethoscope, Tongs) frequency values.**

**The subject is also asked to name the fingers on his/her dominant hand.**

- ☛ Use the study worksheet to record the subject's responses.
- ☛ Objects should be presented in random order. Do not allow the subject to touch the objects.

Give the subject instructions similar to the following:	“Now I am going to show you some objects. I want you to tell me what their names are. What is this called?” (present object)
Continue to present objects in random order. The first question about each object should be:	“What is this called?” or “What is the name of this thing?”
If the subject responds with the object's function say:	“Yes, that's what it does, but what is its name?”

- ☛ If the subject does not respond, the examiner should give the clue for that item provided below. If the subject still does not respond or makes an error, go on to the next object.

ITEM	CLUES
Flower	grows in a garden
Bed	used for sleeping in
Whistle	makes a sound when you blow on it
Pencil	used for writing
Rattle	a baby's toy
Mask	hides your face
Scissors	cuts paper
Comb	used on hair
Wallet	holds your money
Harmonica	a musical instrument
Stethoscope	doctor uses it to listen to your heart
Tongs	picks up food

# ADAS

## INSTRUCTIONS for NAMING TASK (Cont'd.)

➲ The subject is also asked to name the fingers of his/her dominant hand (e.g., thumb, index [pointer/forefinger], middle, ring finger, and pinky).

Give the subject instructions similar to the following:	“Now I am going to point to a part of your hand and I want you to tell me what it’s called. What is this?”						
For the 4 fingers, if a query is necessary, say:	“What is another name for this finger?”						

ITEM	

Thumb	

Index/forefinger/pointer	

Middle	

Ring	

Pinky	

		ITEM	Thumb	Index/forefinger/pointer	Middle	Ring	Pinky
ITEM							
Thumb							
Index/forefinger/pointer							
Middle							
Ring							
Pinky							

The hardest part of scoring the naming task is determination of the range of correct responses based on the subject's cultural and geographical background. A response other than the name given on the response form should be scored as correct if it is a name that would be used by a non-demented person with the same cultural background as the subject.

**FOR EXAMPLE:** the **Mask** might be called a “**false face**” in some parts of the U.S.; the **Wallet** might be called a “**billfold**” or the **Harmonica** might be called a “**mouth organ**”.

➲ Descriptions of the object, semantic or phonemic paraphasias should not be scored as correct.

**EXAMPLES OF INCORRECT RESPONSES ARE:** “**listening thing**” for **Stethoscope**,  
“**cutter**” for **Scissors**, and  
“**prongs**” for **Tongs**.

### SCORING

0 = 0-2	items (objects and fingers) named incorrectly
1 = 3-5	items (objects and fingers) named incorrectly
2 = 6-8	items (objects and fingers) named incorrectly
3 = 9-11	items (objects and fingers) named incorrectly
4 = 12-14	items (objects and fingers) named incorrectly
5 = 15-17	items (objects and fingers) named incorrectly

**Enter the subject's score on the study worksheet.**

## INSTRUCTIONS for COMMANDS

This task is designed to assess receptive speech. The subject is asked to carry out 5 separate commands with 1 to 5 steps per command.

- ⌚ Each command should be read once. If the subject does not respond or makes an error, the tester should give the **ENTIRE** command one more time.
- ⌚ All commands should be given to every subject.
- ⌚ If the subject demonstrates hearing or attentional difficulties, orient them by saying, “**Ready?**” or “**Now I want you to...**” prior to giving the command. Do **NOT** give the command more than twice.
- ⌚ There should be no other materials near the pencil, watch and card (pens, paper, etc.)
- ⌚ Each underlined element represents a single step.
- ⌚ Each command is scored as a whole (no partial credit). All components must be correct for the response to be scored as correct.
- ⌚ Use the study worksheet to record the subject’s responses.

Give the subject instructions similar to the following:	
“Now I am going to ask you to do a few things. First, ...
 
“Make a FIST.” (“Relax it” if needed)
 
“Point to the CEILING and then to the FLOOR.”

Line up a Pencil, Watch, and Card on the table. Say:	
“Put the PENCIL ON TOP OF THE CARD and then PUT IT BACK.”
 
“Put the WATCH on the OTHER SIDE OF THE PENCIL and then TURN OVER THE CARD.”

Remove the Pencil, Watch, and Card from the table. Say:	
“TAP EACH SHOULDER TWICE with TWO FINGERS keeping your EYES SHUT.”

### SCORING

0 =	All commands correct
1 =	1 command incorrect, 4 commands correct
2 =	2 commands incorrect, 3 commands correct
3 =	3 commands incorrect, 2 commands correct
4 =	4 commands incorrect, 1 command correct
5 =	All 5 commands correct

Enter the subject’s score on the study worksheet

[figure not shown]
[figure not shown]
[figure not shown]
[figure not shown]

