### **3.12 Stopping Rules**

This study will be stopped for any of the following reasons

- 1) Any patient death attributed to treatment
- 2) Any patient who develops a Grade IV adverse event
- 3) More than 3 of 15 patients who develop a Grade 3 adverse event as per CTCAE v.5.0 in either group
- 4) 50% or more patients in either group have no change or increase in amyloid based on Amyvid PET Scan

- 5) 5 patients that show greater than 4 point deterioration in MMSE in two consecutive cognition evaluations
- 6) 5 patients that show increases greater than 7 on ADAS-Cog scale.

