
2. NAMING OBJECTS AND FINGERS: Check each object/finger named correctly or check "NONE."
 
 
 NONE 	NONE 	NONE 	
 
  Flower	 Rattle	 Wallet	
 
  Bed	 Mask	 Harmonica	
 
  Whistle	 Scissors	 Stethoscope	
 
  Pencil	 Comb	 Tongs	
 
  Thumb	 Index	 Ring	
 
  Pinky	 Middle		
 
			NONE 	NONE 	NONE 	 Flower	 Rattle	 Wallet	 Bed	 Mask	 Harmonica	 Whistle	 Scissors	 Stethoscope	 Pencil	 Comb	 Tongs	 Thumb	 Index	 Ring	 Pinky	 Middle		
8. LANGUAGE: Check level of impairment.
 
 
 None: patient speaks clearly and/or is understandable.
 
 Very Mild: one instance of lack of understandability.
 
 Mild: patient has difficulty < 25% of the time.
 
 Moderate: patient has difficulty 25–50% of the time.
 
 Moderately Severe: patient has difficulty more than 50% of the time.
 
 Severe: one- or two-word utterances; fluent, but empty speech; mute.
 
													

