
3. COMMANDS: Check each command performed correctly or check "NONE."
 
 
 NONE 		
 
  Make a fist.		
 
  Point to the ceiling, then to the floor.		
 
  Put the pencil on top of the card, then put it back.		
 
  Put the watch on the other side of the pencil and turn over the card.		
 
  Tap each shoulder twice with two fingers keeping your eyes shut.		
 
			NONE 			 Make a fist.			 Point to the ceiling , then to the floor .			 Put the pencil on top of the card , then put it back .			 Put the watch on the other side of the pencil and turn over the card .			 Tap each shoulder twice with two fingers keeping your eyes shut .			
9. COMPREHENSION OF SPOKEN LANGUAGE: Check level of impairment
 
 
 None: patient understands.
 
 Very Mild: one instance of misunderstanding.
 
 Mild: 3–5 instances of misunderstanding.
 
 Moderate: requires several repetitions and rephrasing.
 
 Moderately Severe: patient only occasionally responds correctly; i.e., yes – no questions.
 
 Severe: patient rarely responds to questions appropriately; not due to poverty of speech.
 
																
NONE 																																					
 Make a fist.																																					

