### SCORING

0 =	No instances when it is difficult to understand the subject
1 =	Very mild – one instance of lack of understandability
2 =	Mild – subject has difficulty less than 25% of the time
3 =	Moderate – subject has difficulty 25-50% of the time
4 =	Moderately severe – subject has difficulty 50% of the time
5 =	Severe – one or two word utterance; fluent, but empty speech; mute

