#### SCORING

0 =	No evidence of poor comprehension
1 =	Very mild – 1 or 2 instances of misunderstanding
2 =	Mild – 3-5 instances of misunderstanding
3 =	Moderate – requires several repetitions and rephrasing
4 =	Moderately severe – subject only occasionally responds correctly, i.e., yes/no questions
5 =	Severe – subject rarely responds to questions appropriately, not due to poverty of speech

Enter the subject's score on the study worksheet

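### The ADAS-Cog Commands scoring table gives a perfect performance both code 0 and code 5 and leaves total failure uncoded; a minor correction is needed before the scale feeds the responder and stopping rules

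*Combined protocol and SAP*

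**What the plan says.** The Commands item asks for five commands, each marked wholly right or wrong. The manual's scoring table starts with 0 for "All commands correct", counts incorrect commands upward to 4 for "4 commands incorrect, 1 command correct", and ends with 5 for "All 5 commands correct". The rater is told to enter the resulting score on the worksheet. The accompanying form (ADAS – Cognitive Behavior, item 3) has a box for each command performed correctly and a box for none. It gives no conversion to a score.

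Manual and form also differ on three rated items:

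- **Spoken Language, moderately severe:** the manual says "subject has difficulty 50% of the time"; form item 8 says "patient has difficulty more than 50% of the time".
- **Comprehension, very mild:** the manual says "1 or 2 instances of misunderstanding"; form item 9 says "one instance of misunderstanding".
- **Word-Finding, moderate and moderately severe:** the manual describes loss of words without comprehension; form item 10 describes it without compensation.

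The ADAS-Cog total is used in two decision rules. Section 3.10 calls a patient a responder if the rise is no more than about 3 points. Section 3.12 stops the study for "5 patients that show increases greater than 7 on ADAS-Cog scale"; the Schema words the same rule in terms of mean increases.

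**The concern.** The manual's table is the only place in the documents where Commands responses are turned into a score, and as printed it is not a function: one performance level has two codes and another has none. Raters, or visits, could resolve this differently. A 5-point artefact at one visit is large beside the limits applied to individual patients, and it can act in either direction. At follow-up it looks like deterioration; at baseline it hides deterioration. Section 3.10 adds that the testers may not be using the ADAS-Cog in other studies, so they may have no outside routine to correct the printed rule. The differences on the three rated items are smaller, but those ratings rest on the tester's judgement, with no item-level responses from which to rebuild them.

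**Working it through.** **1. The table as printed, and with the score-5 label changed to incorrect**

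| Commands correct | Code as printed | Code with label corrected |
|---|---|---|
| 5 | 0 and 5 | 0 |
| 4 | 1 | 1 |
| 3 | 2 | 2 |
| 2 | 3 | 3 |
| 1 | 4 | 4 |
| 0 | none | 5 |

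With that one change the table is one-to-one.

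**2. Which label is wrong.** Section 3.10 states that a higher ADAS-Cog score means greater dysfunction. Rows 1 to 4 of the table count errors upward. Ideational Praxis, the other 0–5 item with five components, gives 5 for failing all five. All three agree with row 0 and contradict row 5.

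**3. The protocol's own limit.** Section 3.10 quotes a placebo group going from 24.2 to 29.9 over one year: 29.9 − 24.2 = 5.7. Half of that is 0.5 × 5.7 = 2.85, which reproduces the responder limit of about 3 points.

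**4. Size of one mis-score.** The largest error is 5 − 0 = 5 points at one visit.

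- Follow-up only: the observed change is the true change + 5. A patient with no true change shows +5 and fails the 3-point limit. The 7-point limit is passed only if the true rise exceeds 7 − 5 = 2 points. The artefact is 5/7 = 71% of that limit.
- Baseline only: the observed change is the true change − 5. A true rise of up to 3 + 5 = 8 points still counts as a response, and a true rise of up to 7 + 5 = 12 points does not count towards rule 6.
- Both visits: +5 − 5 = 0, so the error cancels.

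**5. Illustration for a patient who is mis-scored.** Assume the change is normal with the mean 5.7 and SD 8.2 quoted in section 3.10, moved by the shift s:

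P(responder) = Φ((3 − 5.7 − s)/8.2); P(rise > 7) = 1 − Φ((7 − 5.7 − s)/8.2)

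| Shift s | P(responder) | P(rise > 7) |
|---|---|---|
| 0 (no error) | Φ(−0.33) = 0.37 | 1 − Φ(0.16) = 0.44 |
| +5 (follow-up only) | Φ(−0.94) = 0.17 | 1 − Φ(−0.45) = 0.67 |
| −5 (baseline only) | Φ(0.28) = 0.61 | 1 − Φ(0.77) = 0.22 |

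These figures are conditional on the error occurring. The documents give no basis for estimating how often it would.

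**6. The other anchors, side by side**

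- Spoken Language: the manual's code 3 covers 25–50% and its code 4 is 50%, so exactly 50% has two codes and anything above 50% has no percentage anchor. The form's wording removes the overlap.
- Comprehension: both sources put 3–5 instances at the mild level. The form's level below that is a single instance, so two instances has no level. The manual's wording closes the gap.
- Word-Finding: comprehension and compensation are different constructs. The manual's own introduction to the item treats circumlocution and near-synonyms as ways round the difficulty, which fits compensation better.

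Confusion between adjacent levels on any of these items is worth about one point.

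**The case against.** The strongest reply is that this is a slip of one word that a competent rater would see through. Row 0 of the same table scores a perfect performance correctly. A rater facing no correct commands has only code 5 left, which is the intended score. Sections 2.3, 2.4 and 3.10 describe the testers as trained, and section 3.10 mentions their limited ADAS-Cog use in order to explain the lack of blinding. It does not say that they will depend on the printed manual. The form preserves the raw responses. A false 5-point rise needs a patient with moderate dementia to perform all five commands at follow-up and a rater to choose code 5 over the row-0 label, without the same error at baseline. Rule 6 also needs five patients, and if the Schema's mean increases are averages over visits, a single-visit error would be diluted. Section 3.1 calls the assessment of endpoints descriptive.

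Most of this stands, and it bears on likelihood and severity. It does not make the table consistent, and a descriptive analysis still uses the responder limit and the stopping rule.

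A reader might infer that the item is reverse-scored, so that patients who perform perfectly receive the worst score. The documents do not support that: row 0 and rows 1 to 4 run in the right direction, and the defect is one contradictory label plus one missing code. A reader might also infer that the manual should simply be made to match the form. For Comprehension that would bring in a gap that the manual does not have.

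**Conclusion.** The Commands table contradicts itself and should be corrected; severity is minor. The effect is bounded at 5 points at one visit. It is enough alone to cross the responder limit of about 3 points, is not enough alone to cross the 7-point limit, and is nil if the same error is made at both visits. The probabilities in the working assume normal change with the quoted placebo mean and SD, and describe a mis-scored patient, not the cohort. That the score-5 label is the faulty one rests on the direction of the scale, rows 0 to 4 and the parallel praxis item, all within the documents. The disagreements on Spoken Language, Comprehension and Word-Finding are real and smaller.

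A reader might compare 5 points with the 5.7-point yearly decline and conclude that a whole year's progression could be an artefact. That sets a conditional maximum for one patient against a group mean, and the documents do not support it as a statement about the trial's results.

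**What to change.** - Change the score-5 label in the Commands table so that it refers to all five commands being incorrect.
- State that the Commands score is derived, or verified, from the boxes checked on form item 3 before the responder definition and stopping rule 6 are applied. If testing has begun, recompute the item from the forms already completed.
- Adopt one set of anchors for manual and form, complete and without overlap: the form's wording for moderately severe Spoken Language, the manual's wording for very mild Comprehension, and a single agreed term for the two Word-Finding levels.
- Tell the testers which document governs if any other difference is found.

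The cost is a few words in an appendix and a short check of one item per visit. Nothing changes in the visits, the instrument, the sample size or the limits themselves.
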